11.6.2. Handling of Missing Data

Element	Reporting Detail
General	 Missing data occurs when any requested data are not provided, leading to blank fields on the collection instrument:
	 These data will be indicated by the use of a "blank" in subject listing displays. Unless all data for a specific visit are missing in which case the data is excluded from the table.
	 Answers such as "Not applicable" and "Not evaluable" are not considered to be missing data and should be displayed as such.
Outliers	Any subjects excluded from the summaries and/or statistical analyses will be documented along with the reason for exclusion in the clinical study report.

11.6.2.1. Handling of Missing and Partial Dates

Element	Reporting Detail
General	Partial dates will be displayed as captured in subject listing displays.

Element	Reporting Detail					
SLE Duration	 If only year of SLE diagnosis is known, day and month will be set to 01 January. If month and year are known, but not the day, the day will be set to 01. 					
Adverse Events	 The EDC does not allow partial dates to be entered for AE start and stop dates. Completely missing start or end dates will remain missing, with no imputation applied. Consequently, time to onset and duration of such events will be missing. AEs with missing start dates will be considered as treatment-emergent. 					
Concomitant Medications	 The EDC allows partial dates to be entered for medication start dates (but the Year must be present). Partial dates cannot be entered for medication end dates. For reporting, missing or partial start and/or end dates will remain missing, with no imputation applied. Medications with partial or missing start dates will be considered as concomitant unless there is evidence through comparison of partial dates to suggest otherwise. For example, if the day is missing, then the month and year will be compared to the month and year of the first dose of belimumab, and if the month and year are the same or later, the medication will be considered concomitant. Medication with missing end dates will be considered 'ongoing'. 					

11.6.2.2. Handling of Missing Data for Statistical Analysis

Element	Reporting Detail
General	 The efficacy endpoints will be summarised using observed case data, for all subjects in the Safety population, unless otherwise stated. Assessments not done will remain as missing.
SLICC/ACR Damage Index	 The Index is cumulative, once an item is scored it should continue to be scored for all subsequent assessments (see Section 11.5.4.4). Where an assessment is completed (at least one item was marked or a total score of 0 was recorded), items left unchecked on the SLICC/ACR, and not previously checked, will be considered as "not present" (rather than missing), and assigned an item score of 0 in the analysis dataset (see Section 11.5.4.4).
SELENA SLEDAI	Where an assessment is completed (at least one item was marked or a total score of 0 was recorded), items left unmarked on the SELENA SLEDAI will be considered as "not present" (rather than missing), and assigned an item score of 0 in the analysis dataset (see Section 11.5.4.1).
BILAG	As OL BILAG assessments are every 6 months vs monthly for the DB part of the parent studies, items left unmarked on the questionnaire will not be imputed. See Section 11.5.4.2, for the derivation of organ domain scores with missing data.

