4.4. Withdrawal Criteria

A subject may voluntarily discontinue participation in this study at any time. The investigator may also, at his or her discretion, discontinue a subject from this study. Every effort should be made by the investigator to keep subjects in the study and to ensure return for the Exit visit 4 weeks after the last dose of belimumab, and the follow-up visits 16 weeks after the last dose. For any subject who had an anti-belimumab antibody response at the 16-week follow-up visit (or last study visit at which immunogenicity was assessed if the 16-week follow-up immunogenicity sample is not available), an attempt will be made to obtain a serum sample for anti-belimumab antibodies at least 6 months after the last dose of study agent. From subjects at selected sites only, B-cell subsets will be collected at the EXIT visit and at approximately 6 months after the last dose of study agent.

Notwithstanding this requirement, the investigator should adjust concurrent medications as clinically required.

Reasons for subject withdrawal include “adverse event”, “lack of efficacy”, “protocol deviation”, “study closed/terminated”, “lost to follow-up”, “investigator discretion”, and “withdrew consent”. The investigator will record the primary reason in the electronic case report form (eCRF) and any data collected up until the point of withdrawal, and the follow-up visits will be used in the analyses.

If a subject is permanently discontinued from belimumab during the course of the study, the subject must be withdrawn from the study. In addition, subjects will be withdrawn from the study if any of the following criteria are met:

- **Unacceptable toxicity** including:
 - **Laboratory parameters:** Demonstrate clinically important changes in laboratory parameters.
 - **Liver Chemistry:** Detailed in Section 6.3.1.
- **Pregnancy:** Positive urine pregnancy test.
- **Concurrent Medication:** Prohibited concurrent medication or therapy (See Section 5.3.2 and Section 5.3.3).
- **Consent:** Withdrawal of consent.
- **Compliance:** Missed 3 or more consecutive study infusions.

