5.3.2. Prohibited Medications and Non-Drug Therapies

Subjects who start prohibited medications or therapies at any time during the study must be withdrawn from treatment with belimumab and enter study follow-up. The following medications and therapies are prohibited at any time during the study:

- Other investigational agents (biologic or non-biologic). Investigational applies to any drug not approved for sale in the country in which it is being used.
- Co-enrolment into another study of an investigational agent or non-drug therapy that may interfere with the conduct of this protocol.
- Anti-TNF or anti-IL-6 therapy (e.g., adalimumab, etanercept, infliximab).
- Other biologics (e.g., rituximab, abatacept, interleukin-1 receptor antagonist [anakinra]).
- Intravenous immunoglobulin (IVIG).
- IV cyclophosphamide.
- Plasmapheresis, leukapheresis.

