- Due to the additional 6 month OL extension for SC subjects entering BEL114333, there is a 6 month off-set in the data capture between the parent studies. As a result, for SLICC, immunoglobulins and B cell subsets, captured on an annual basis in BEL114333, the data captured at each analysis visit stratifies by parent study. As such these endpoints will be tabulated by parent study, and the data will not be aggregated.
- Summaries by belimumab Treatment: Data will be mapped to the year by windowing starting at the time of first belimumab treatment.

The GlaxoSmithKline group of companies

BEL114333

- Listings: If endpoints reported, data will be presented in listings as required.
- Figures: error bars will be displayed.

Unless otherwise stated, no imputation for missing values will be conducted.

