8.1.1. SRI Response Rate

The proportion of subjects achieving an SRI response will be summarised by parent randomised treatment group, and the total Safety population, for each belimumab visit (every Week 24 and Week 48 visit). Total Safety population data will be displayed graphically using a line graph.

The SRI response is defined as:

- ≥ 4 point reduction from baseline in SELENA SLEDAI score, **AND**
- No worsening (increase of < 0.30 points from baseline) in Physician's Global Assessment (PGA), AND

• No new British Isles Lupus Assessment Group of SLE Clinics (BILAG) A organ domain score or 2 new BILAG B organ domain scores compared with baseline at the time of assessment.

Note: This third bullet is more clearly written as, "No new British Isles Lupus Assessment Group of SLE Clinics (BILAG) A organ domain score and at most 1 new BILAG B organ domain score compared with baseline at the time of assessment."

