8.1.2. SELENA SLEDAI ≥ 4 Point Reduction from Baseline

The proportion of subjects with a reduction from baseline of ≥ 4 points in SELENA SLEDAI score will be summarised by parent randomised treatment group, and the total Safety population, for each belimumab visit (every Week 24 and Week 48 visit). Total Safety population data will be displayed graphically using a line graph.

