11.6. Appendix 6: Premature Withdrawals & Handling of Missing Data

11.6.1. Premature Withdrawals and Completion

Element	Reporting Detail
General	 All subjects were indicated as withdrawn from study BEL114333 based on the design of the end of treatment CRF page. Study completion (i.e. as specified in the protocol) is defined as the subject was still participating in the study at the time belimumab became commercially available in Japan and Korea * or the subject transferred to a different protocol (as indicated by a reason for withdrawal of Investigator Discretion), or upon the decision by the sponsor to close/terminate the study (as indicated by a reason for withdrawal of Study/Closed Terminated).
	 * the study is now being closed as PMDA approved Benlysta, and subjects have been transitioned from study supplied belimumab over to commercially available Benlysta. The KFDA approved Benlysta in 2015. • There will be no adjustments for missing results (i.e. LOCF) due to subject withdrawal prior to study termination. • All subjects are expected to return for an exit visit. Subjects no longer receiving belimumab after their exit visit are expected to return for follow up visits. See Section 2.3 for more details. • All available data will be listed and all available planned data will be included in summary tables and figures, unless otherwise specified.

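### Observed-case SRI and 4-point SELENA SLEDAI rates drop a failing subject after at most one more visit, so the long-term curves can rise by selection if non-responders withdraw faster

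*SAP*

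**What the plan says.** The missing-data rule for efficacy is in SAP 11.6.2.2: "The efficacy endpoints will be summarised using observed case data, for all subjects in the Safety population, unless otherwise stated". It adds: "Assessments not done will remain as missing". SAP 11.6.1 says: "There will be no adjustments for missing results (i.e. LOCF) due to subject withdrawal prior to study termination". The general rule in SAP 5.1 agrees: "Unless otherwise stated, no imputation for missing values will be conducted".

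The two endpoint sections make no exception. SAP 8.1.1: "The proportion of subjects achieving an SRI response will be summarised by parent randomised treatment group". SAP 8.1.2: "The proportion of subjects with a reduction from baseline of ≥ 4 points in SELENA SLEDAI score will be summarised". Both apply at every Week 24 and Week 48 belimumab visit, with a line graph for the total Safety population. The display lists in SAP 11.12.6 and 11.12.7 contain no non-responder or treatment-failure version.

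Three other provisions decide who is in each denominator:

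- Protocol 4.4 includes "lack of efficacy" among the withdrawal reasons and makes permanent discontinuation of belimumab a withdrawal from the study. Protocol 5.3.2 adds: "Subjects who start prohibited medications or therapies at any time during the study must be withdrawn from treatment with belimumab and enter study follow-up".
- The disease activity scales are scheduled at the Exit visit, about 4 weeks after the last dose, and not after it (Protocol Tables 2 and 3). SAP 5.1 assigns Exit efficacy data to the next 6-monthly visit of that year.
- SAP 11.6.1 separates completion (commercial availability, transfer to another protocol, sponsor closure) from withdrawal. The efficacy rates do not use this split.

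**The concern.** Some exits are tied to outcome by design. Subjects who leave for lack of efficacy, or who start a therapy such as IV cyclophosphamide or rituximab that ends their belimumab treatment, are mostly not responders. After the visit that holds their Exit assessment they contribute nothing, so later percentages describe an increasingly selected group.

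Long-term efficacy is the secondary objective, and SAP Table 1 makes SRI a key secondary endpoint. The same table says that the graphs are meant to show response over time. A curve that climbs because non-responders have left would be read as sustained or growing benefit.

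**Working it through.** The documents state no expected response rate, dropout rate, sample size or power, so there is no planned figure to reproduce. The check isolates selection by fixing each subject's response status.

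**Inputs**

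- Observed cases, no adjustment for withdrawal: SAP 11.6.2.2, 11.6.1 and 5.1.
- Exit data count at the next 6-monthly visit: SAP 5.1.
- Follow-up runs from the first belimumab dose (SAP 2.4.1), but the Safety population needs at least one IV dose in BEL114333 (SAP 4), hence completion of the parent study.
- Assumed, not in the documents: response p = 50%; yearly withdrawal wR = 4% in responders and wN = 12% in non-responders.

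**Time at risk.** Let y be the belimumab year and t the years in which a subject can leave the Safety population. BEL113750 belimumab subjects cannot leave in their first year, so t = y − 1. BEL113750 placebo subjects start belimumab at BEL114333 Day 0, so t = y. BEL112341 subjects cannot leave for about 18 months (belimumab) or 6 months (placebo).

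**Formula.** Observed-case rate = p(1 − wR)^t / [p(1 − wR)^t + (1 − p)(1 − wN)^t]. The Exit rule delays each departure by one half-yearly visit, so t becomes t − 0.5.

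**BEL113750 belimumab subjects**

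- Year 3, t = 2: 0.9216 / (0.9216 + 0.7744) = 54.3%. With the Exit rule, t = 1.5: 53.3%.
- Year 5, t = 4: 0.8493 / (0.8493 + 0.5997) = 58.6%. With the Exit rule, t = 3.5: 57.6%.

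**BEL113750 placebo subjects** (t = y): 56.5% at Year 3 and 60.7% at Year 5; with the Exit rule 55.4% and 59.7%.

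**Range**, BEL113750 belimumab subjects at Year 5, p = 50%:

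| Yearly withdrawal, responders / non-responders | Without Exit rule | With Exit rule |
|---|---|---|
| equal | 50.0% | 50.0% |
| 5% / 10% | 55.4% | 54.7% |
| 3% / 9% | 56.4% | 55.6% |
| 4% / 12% | 58.6% | 57.6% |
| 5% / 15% | 60.9% | 59.6% |
| 5% / 20% | 66.5% | 64.6% |

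**Effect of a correction**, 4% / 12%, Year 5, taking the 4% common to both groups as administrative:

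- Failures kept as non-responders, administrative exits removed: 0.5 × 0.96^4 / (0.5 × 0.96^4 + 0.5 × 0.96^4) = 50.0%, the true value.
- Every exit counted as non-response: 50% × 0.96^4 = 42.5%, which overcorrects.

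**The case against.** The study is open-label with a safety primary objective, and every analysis is descriptive (Protocol 8, SAP 2.4). No error rate or decision rule depends on these curves. Attrition is also visible elsewhere: SAP Table 3 plans completion status and withdrawal reasons by year, plus a Kaplan-Meier display of time to withdrawal, and categorical summaries report n. This limits the weight of the point. It does not answer it, because those displays never enter the response rates and a reader cannot recover a corrected rate from them.

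Many exits are administrative. Korean sites closed in 2015, and other subjects transferred or moved to commercial supply (SAP 3.2, 11.6.1). Protocol 4.4 also lists reasons unrelated to response, such as withdrawn consent and loss to follow-up. This stands, and it rules out treating every missing value as non-response.

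The SELENA SLEDAI and BILAG derivations are redacted and the mock shells are in a separate document, so an exception there cannot be excluded. The reference to all Safety subjects might even suggest a fixed denominator, although observed cases with missing values left missing point the other way.

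A reader might infer that withdrawn subjects supply nothing once off drug, so that each rate covers only subjects still on treatment. SAP 5.1 contradicts this, because a subject who attends Exit is counted once more. A reader might also apply attrition to everyone from the first belimumab dose. Among BEL113750 subjects that fits only those randomised to placebo; for the belimumab group it overstates Year 3 and Year 5 by about 2 points each (56.5% against 54.3%, and 60.7% against 58.6%).

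**Conclusion.** The point holds as a possibility built into the plan. After at most one further visit, a failing subject leaves the SRI and SELENA SLEDAI denominators, and no visible supportive analysis keeps that subject in. The curve drifts upward only if non-responders withdraw faster than responders. The documents do not establish that they did, so they do not support saying that the curve is biased or will rise.

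Under the assumed 4% and 12%, the drift for BEL113750 belimumab subjects is about 4 points at Year 3 and 9 points at Year 5, and about 1 point less with the Exit rule. Across the unequal rates tabulated, it is about 5 to 17 points at Year 5. These figures assume fixed response status and constant withdrawal rates. The consequence is for interpretation of the secondary efficacy displays only, and the correction is a cheap improvement.

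**What to change.** Keep the observed-case result. Add one supportive row to Tables 3.1 and 3.2 and one line to Figures 3.1 and 3.2, defined as follows.

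- **Counted as non-responders:** subjects withdrawn for lack of efficacy or adverse event, subjects withdrawn after starting a prohibited therapy, and deaths. Protocol 4.4 has no separate reason for prohibited therapy, so identify these from the concomitant medication records.
- **At which visits:** each Week 24 and Week 48 visit after the one holding the Exit assessment, up to the last visit that the subject could have reached given their own first belimumab dose date and their country's closure date. State those closure dates in the SAP. Using each subject's own limit avoids holding late entrants who failed in denominators that late entrants who completed have already left.
- **Leave the denominator after their last assessment:** per-protocol completers (country closure, confirmed transfer, sponsor closure) and withdrawals for other reasons.
- **Investigator Discretion:** SAP 11.6.1 uses this reason to mark transfers, but Protocol 4.4 lists it as a general withdrawal reason. Count it as completion only where transfer to another protocol is confirmed.

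Print the number observed and the number counted as failures at each visit, and state the observed-case denominator in SAP 8.1.1 and 8.1.2.

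The cost is SAP wording, a check of Investigator Discretion exits and concomitant medication records, and one row or line in four existing displays. No new data are collected. The supportive rate will be less favourable than the observed-case rate.

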6.2. Efficacy

6.2.1. Efficacy Endpoints

6.2.1.1. Primary Endpoint

The primary efficacy endpoint is response rate at each scheduled visit when complete efficacy evaluations occur (e.g., Weeks 24 and 48 of Year 1 and Year 2, etc).

- A response is defined as:
 - ≥ 4 point reduction from baseline in SELENA SLEDAI score,AND
 - No worsening (increase of < 0.30 points from baseline) in Physician's Global Assessment (PGA),AND

- No new BILAG A organ domain score or 2 new BILAG B organ domain scores compared with baseline at the time of assessment (i.e., Weeks 24 and 48 of Year 1 and Year 2, etc).

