6.2.2.1. SELENA SLEDAI Score

The SLEDAI (Systemic Lupus Erythematosus Disease Activity Index) is a validated index for assessing SLE disease activity [[Bombardier, 1992](#)]. It is a weighted index in which signs and symptoms, laboratory tests, and physician's assessment for each of 9 organ systems are given a weighted score and summed, if present at the time of the visit or in the preceding 10 days:

- Score of 8 each for CNS and vascular items.
- Score of 4 each for renal and musculoskeletal items.
- Score of 2 each for serosal, dermal, and immunologic items.
- Score of 1 each for constitutional and hematologic items.

The SELENA SLEDAI used in this study is a slightly modified version of the SLEDAI developed for a National Institutes of Health sponsored multicentre study of estrogen/progesterone hormone use in women with SLE [[Buyon, 2005](#); [Petri, 2005](#)]. The descriptions for some of the items are slightly modified, but the organ systems and weighted scores are the same as the SLEDAI. The maximum theoretical score for the

SELENA SLEDAI is 105 (all 24 descriptors present simultaneously) with 0 indicating inactive disease. Completion of the index requires collection of a 24-hour urine sample for assessment of proteinuria (although spot urine protein:creatinine ratio is commonly substituted in practice, see Section 6.2.2.2), measurement of anti-dsDNA, C3, C4, haematology, and urinalysis, and for subjects with myositis, CPK. Guidelines for scoring proteinuria are provided in Section 6.2.2.3.

SELENA SLEDAI will be assessed at Day 0 and then every 24 weeks thereafter.

A copy of the index is provided in [Appendix 1](#).

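### SAP 11.6.2.2 scores unmarked SELENA SLEDAI items 0 without separating a negative laboratory item from one with no result, which can by itself create a 4-point fall

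*SAP*

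**What the plan says.** SAP Section 11.6.2.2 gives the general efficacy rule as observed cases: "Assessments not done will remain as missing". It then sets item-level rules by instrument. The SELENA SLEDAI rule is triggered by "Where an assessment is completed (at least one item was marked or a total score of 0 was recorded"), and from that point "items left unmarked on the SELENA SLEDAI will be considered as 'not present' (rather than missing), and assigned an item score of 0". Whether a laboratory result exists is not a condition. For BILAG the same table says that "items left unmarked on the questionnaire will not be imputed".

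Protocol Section 6.2.2.1 says that completing the index needs a urine protein measurement together with "measurement of anti-dsDNA, C3, C4, haematology, and urinalysis, and for subjects with myositis, CPK". It also gives the weights: "Score of 4 each for renal and musculoskeletal items"; "Score of 2 each for serosal, dermal, and immunologic items"; and 1 for each haematologic item. Protocol Section 6.2.2.3.1 adds that a subject already carrying 4 points for proteinuria drops to 0 only after a measured improvement, and otherwise keeps the 4.

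The first of the three SRI components is "≥ 4 point reduction from baseline in SELENA SLEDAI score". SAP Section 8.1.2 also analyses that fall as an endpoint of its own.

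**The concern.** For a clinical item, a blank box is reasonably read as absent. For a laboratory item, a blank can mean that the result was negative or that there was no result. Protocol Section 6.3.8 sends blood samples to a central laboratory, so results come back after the visit and a site can complete the clinical items before they arrive. If a sample is lost or unusable and the box stays blank, the visible rule records the abnormality as resolved.

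After baseline, the substitution can lower a score but never raise it. A missing result can therefore appear as improvement in the long-term efficacy tables, and a reader of those tables could not tell a measured resolution from a missing sample.

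**Working it through.** The plan has no sample size or power figure to reproduce. The check applies the SAP rule to the protocol's weights.

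**Inputs**
- Weights (Protocol 6.2.2.1): renal 4, immunologic 2, dermal 2, haematologic 1. Low complement and anti-dsDNA are taken as two immunologic items; the scoring form itself is withheld.
- Threshold (SAP 8.1.1 and 8.1.2): fall of at least 4.
- Rule (SAP 11.6.2.2): unmarked = 0.

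**Step 1: unchanged subject.** Baseline = proteinuria 4 + low complement 2 + anti-dsDNA 2 + one dermal item 2 = 10. At the later visit the true score is still 10 and the dermal item is marked, so the rule applies. Fall = 10 − score under the rule.

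| Results missing and items left blank | Score under the rule | Fall | Fall ≥ 4? |
|---|---|---|---|
| None | 10 | 0 | No |
| Urine protein | 10 − 4 = 6 | 4 | Yes |
| Complement and anti-dsDNA | 10 − (2 + 2) = 6 | 4 | Yes |
| One immunologic result only | 10 − 2 = 8 | 2 | No |

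Haematology alone would need four positive items (4 / 1 = 4).

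**Step 2: missing at baseline instead.** If the urine result is missing at baseline, the recorded baseline is 10 − 4 = 6. A true later fall from 10 to 6 then shows as 6 − 6 = 0, and a real response is hidden.

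**Step 3: from the fall to SRI.** SRI also needs a PGA increase below 0.30, no new BILAG A and at most one new BILAG B. An unchanged subject meets both conditions if they are evaluable. Protocol Section 6.2.2.2 uses the urine protein ratio for BILAG as well, so a lost urine sample might leave SRI not evaluable. The visible text does not tie complement or anti-dsDNA to BILAG.

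**Step 4: illustrative size.** The documents give none of these inputs; all are assumed.
- q, share of visits with the result missing and the item blank: 1% to 10%
- s, share of subjects with at least 4 baseline points on that sample: 20% to 60%
- t, true response rate: 40% to 60%
- p, share of the rest meeting the PGA and BILAG conditions: 70% to 95%

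Added SRI response = q × s × (1 − t) × p.
- Low: 0.01 × 0.20 × 0.40 × 0.70 = 0.00056, about 0.06 percentage points.
- High: 0.10 × 0.60 × 0.60 × 0.95 = 0.0342, about 3.4 percentage points.

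For the ≥4-point endpoint alone, without p and reading t as its own true rate, the range is 0.01 × 0.20 × 0.40 = 0.08 points to 0.10 × 0.60 × 0.60 = 3.6 points. The formula treats the factors as independent and takes each exposed non-responder as otherwise unchanged.

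**The case against.** The strongest reply is that the SLEDAI row points to SAP Section 11.5.4.1, which is withheld for copyright and may contain a safeguard. A reader might infer that the SAP positively instructs a 0 where the laboratory result is missing. It does not say that; the point rests on a stated rule with no visible exception. This objection stands as a limit on certainty, and the fix allows for it.

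A reader might also infer that the 4-point fall defines SRI response, or that missing laboratory data always favours belimumab. Neither is supported. The fall is one of three SRI components. A missing result changes nothing when the item would have been negative or the subject has no points at stake, and at baseline it works against response.

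Other replies stand in part:
- A site following Protocol Section 6.2.2.3.1 should not drop the proteinuria points without a result. That makes the proteinuria case less likely, but it also shows that the SAP gives a blank the 0 that the protocol reserves for measured improvement.
- SLEDAI counts what is present, and the SAP gives BILAG its own reason, the change to six-monthly assessment. The contrast with BILAG is therefore weak support, and the general rule on assessments not done concerns whole assessments.
- Scorers pass proficiency tests, results are faxed to investigators and the database is cleaned before analysis. These steps should make such blanks less common; none of them changes the rule.
- The analyses are descriptive and efficacy is secondary, so no test is affected. The reported response rates still are.

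**Conclusion.** The concern holds in a limited form. As visible, the rule cannot tell a negative laboratory item from one with no result, and with the protocol's weights it can produce a 4-point fall in a subject whose disease has not changed. Three things must coincide: baseline points on the affected items, no result after baseline, and a blank left by the site on an assessment that otherwise counts as completed.

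The effect is direct on Tables 3.2, 3.8 and 3.9. In Table 3.1 it supplies one of three required components. The error is 4 points for a missing urine protein result or for both immunologic results together, and 2 for one immunologic result. The frequency is unknown, so the percentage-point range is an illustration and not an estimate. The conclusion assumes that the withheld section holds no safeguard.

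**What to change.** Keep the present rule for clinical items. For laboratory-dependent items (complement, anti-dsDNA, urine items, platelets, leukocytes and CPK-based myositis), treat an unmarked item as not evaluable when no result is available for that visit. Accept any available result, not only a central one.

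- Set the total score to missing for that visit.
- Set the ≥4-point status and SRI to missing only if the unresolved item could change them. Compute the fall with the item at 0 and at its full weight. In the lost-urine example the range is 0 to 4, so the status is missing. If the urine and both immunologic items had truly resolved (fall 4 + 2 + 2 = 8) and one haematologic item had no result, the range is 7 to 8 and the threshold is met either way. If PGA or BILAG already fails, SRI is a non-response regardless.
- Apply the same rule at baseline, after using the last available pre-dose value under SAP Section 11.4.2.
- Footnote the number affected in Tables 3.1, 3.2, 3.8 and 3.9.

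If Section 11.5.4.1 already does this, one sentence in Section 11.6.2.2 is enough.

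The cost is SAP wording and a merge with laboratory data already in the analysis database. A few visits become non-evaluable. A few subjects may have no evaluable baseline, and under SAP Section 11.4.2.4 they would drop out of the change-from-baseline summaries.
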